8.1 Trial management group

A Trial Management Group (TMG) composed of research members will oversee the feasibility trial. Members will include the Chief Investigators, trial manager, health economist etc.

TMG will meet frequently during both the set-up and running of the trial. Once the trial begins, TMG will monitor the different aspects of the trial such as recruitment, and data collection. They will also ensure that trial protocol is followed.

8.2 Patient and public involvement

We will work in partnership with carers and people with Parkinson's, to improve the relevance, quality, and impact of the iSupport-PD feasibility study. We have also involved a PPI advisory panel, with the PPI lead (JM) being a member of the research team. The PPI team consist of care partners of people with Parkinson's and have a range of experience. The PPI team have advised on the iSupport-PD design. In addition, for WS2 and WS3 they have been involved in co-production of data collection materials and approaches to recruitment.

All study participants will be offered a £10 gift voucher at the end of the study as a thank you for taking part. Each participant that is interviewed will also receive an additional £10 voucher as a thank you for taking part.

Any updates on our study will posted on our study website https://hosting.northumbria.ac.uk/isupportpd/, which is available to the public.

9. Ethics and regulatory approvals

Ethical approval will be sort by Northumbria University and the NHS REC.

10 Monitoring

10.1 Quality assurance and Quality Control of data

Trial processed and data will be monitored throughout the trial with updated provided monthly at the trial management group meetings. Data collected during the course of the trial will be checked during the trial to offer quality assurance. As this is a feasibility trial, quality assurance will also allow the team to assess issues such as incomplete data collection forms, which may suggest misunderstanding, unwillingness to complete certain questions, or misunderstanding of data collection forms. This will contribute to the findings of the feasibility study and allow flexibility and changes to trial processes during the trial (with changes to the protocol noted and ethical approval for adjustments sought where necessary.

10.2 Monitoring plan

A Monitoring Plan will be prepared prior to participant recruitment detailing the monitoring strategy for the feasibility study and corresponding cost-effectiveness analysis (WS2 and WS3). The plan will include requirements for day-to-day centralised monitoring of the trial and any additional safety requirements.

10.3 Study end date

Study end date, defined as the last point of data collection, will be 31st October 2025. No further data collection will occur after this point and the data will be 'locked' to allow final analysis. The Research Ethics Committee will be notified of the study end date within 90 days. Following study end date, the final report will be submitted to the Research Ethics Committee within 12 months of the end of study.

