Development and Feasibility Trial of iSupport-PD, a Digital Intervention for carers of people with Parkinson's and cognitive impairment

iSupport-PD

Study Protocol

Version 2.1

FULL/LONG TITLE OF THE STUDY
Development and Feasibility Trial of iSupport-PD, a Digital Intervention for carers of people with Parkinson'
and cognitive impairment

SHORT STUDY TITLE / ACRONYM

iSupport-PD

PROTOCOL VERSION NUMBER AND DATE:

Version 2.1

January 2025

RESEARCH REFERENCE NUMBERS

IRAS Number: 325361

SPONSORS Number: [name] 2024-0217-6596

FUNDERS Number: NIHR204259

KEY STUDY CONTACTS

Chief Investigators	[name] & [name]
Study Co-ordinator	[name]
Sponsor	Northumbria University
Joint-sponsor(s)/co-sponsor(s)	University of Southampton
Funder(s)	National institute of Health Research (NIHR) Research for patient benefit (RFPB) Research for Social Care funding stream (RfSC)

Co-Investigators

Name	Organization	Contact
[name]	Northumbria University, Assistant professor Health Economics, Statistician	[contact]
[name]	University of Southampton, Research Fellow	[contact]
[name]	Northumbria University, Assistant [name]	[contact]
[name]	Expert by experience	[contact]
[name]	Northumbria University, Senior research associate	[contact]

STUDY SUMMARY

Study Title	Development and Feasibility Trial of iSupport-PD, a Digital Intervention for carers of people with Parkinson's and cognitive impairment
Internal ref. no. (or short title)	iSupport-PD
Study Design	Feasibility RCT, mixed methods design
Study Participants	Care partners of people with Parkinson's and cognitive impairment
Planned Size of Sample (if applicable)	100
Follow up duration (if applicable)	12 months
Planned Study Period	12 months
Research Question/Aim(s)	To explore the feasibility of a randomised controlled trial (RCT) for iSupport-PD and the acceptability of the intervention

ROLE OF STUDY SPONSOR AND FUNDER

Northumbria University assume overall responsibility for the ethical governance of the study.

ROLES AND RESPONSIBILITIES

Trial Management Group

The study management committee, comprising of leads and co-applications will meet on a monthly basis.

Patient and Public Involvement Group

We will also consult with our lay advisory group to gain their feedback on intervention content, suggested modifications, recruitment materials, and interview topic guides. This group, led by the PPI lead will meet on a quarterly basis.

Stakeholder involvement

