4.7 Data collection

The primary mode of data collection for surveys will be technology mediated. Participants will be sent a personalised link to self-complete questionnaires online which were developed using Qualtrics. Data will be collected at baseline, 3 months after baseline (T1), 6 months after baseline (T2), and 12 months after baseline (T3) (depending on when the participant was recruited into the study). The baseline measures will be collected prior to randomisation and will include demographic data such as age, gender, ethnicity, marital status, sexual orientation, socioeconomic status, education level, carer relationship, usual carer support, length of caring. Where data collection surveys are not completed a reminder will be sent via email to prompt participants to complete. After this, researchers will contact participants and collect data through interview via telephone or internet-based service (e.g. Zoom or Teams). Although effort will be made to obtain follow-up data as close as possible to the relevant timepoints, it is anticipated that there may be some variation. T1, T2, and T3 follow-up will be acceptable up to 2 weeks early and 4 weeks late.

Data will be collected through the iSupport-PD study website, through an electronic case report form (CRF) with data stored on a secure password protected, purposely designed electronic database. Each participant will be randomly assigned a trial identify code at the point of their randomisation for use on CRF forms, electronic database, and other trial documentation. CRF data and electronic forms will be treated as confidential documents and held securely in accordance with regulations. The researcher will make an independent, separate, and confidential, record of participant name, age, date of birth, and trial number to permit identification of all trial participants as needed.

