4.8 Data analysis

Analysis of outcome data will be conducted using an intention to treat approach, with patients analysed according to their treatment assignment. It will not be possible to collect outcome data for those who discontinue participation in the study. The data collected from outcome measures will be presented using

summary statistics (number of responses, mean ± standard deviation (SD), percentage frequency) and differences between intervention and control calculated at each follow-up points along with 95% confidence intervals. As this is a feasibility study, it will not be powered to identify significant differences between intervention and control. However, this data will help inform treatment effect estimates and sample size requirements for a larger powered RCT.

Feasibility of a future RCT will be investigated using progression criteria designed according to The Consolidated Standards of Reporting Trials (CONSORT) extension for reporting feasibility trials (38). This will enable interpretation of the findings of the feasibility study and inform whether a larger powered RCT is possible. Progression criteria will be assessed on a traffic light system of green/amber/red zones (39). Successful outcome of the feasibility trial would be to have all criteria assessed as green zones, suggesting no adjustments would be required for a future RCT. It is anticipated that progression to a future RCT would still be possible with a combination of amber and green zones but with potential adjustments implemented to mitigate risks highlighted in this feasibility study. Any red zone criteria would indicate that either the RCT trial design, or processes, will need to be overhauled for any future definitive study. All thresholds have been set based on levels that would enable completion of the trial objectives (Green without adaptation, Amber with adaptations to trial processes, Red/stop would not be possible to complete):

Criteria	Green	Amber	Red
Recruitment of participants based on target of n=100	>75	50 - 74	<=50
	(75%)	(50 - 74%)	(<50%)
Intervention engagement: assessed by number of intervention	>=70%	50-69%	50%
participants who have used iSupport-PD			
Recruited participants completing 3-month follow-up	>=75%	50-74%	<50%.
Recruited participants completing 6-month follow-up	>=75%	50-74%	<50%.
Recruited participants completing 12-month follow-up	>=75%	50-74%	<50%.

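### The follow-up progression criteria count every recruited participant, although the fixed end of data collection puts the 12-month visit out of reach for anyone with a baseline after 14 November 2024

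*Protocol*

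**What the plan says.** Three parts of the protocol bear on this.

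- **End of data collection (section 10.3).** "Study end date, defined as the last point of data collection, will be 31st October 2025". The stop is firm: "No further data collection will occur after this point and the data will be 'locked' to allow final analysis".
- **Visit schedule (section 4.7).** T1, T2 and T3 fall 3, 6 and 12 months after baseline. T3 is given with a qualifier: "12 months after baseline (T3) (depending on when the participant was recruited into the study". The window is common to all three visits: "T1, T2, and T3 follow-up will be acceptable up to 2 weeks early and 4 weeks late".
- **Progression criteria (section 4.8).** The 12-month row is labelled "Recruited participants completing 12-month follow-up", and the 3- and 6-month rows are worded in the same way. All three are green at 75% or more, amber at 50 to 74% and red below 50%. On red, the section says: "Any red zone criteria would indicate that either the RCT trial design, or processes, will need to be overhauled for any future definitive study".

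The study summary gives 12 months for the follow-up duration and also 12 months for the "Planned Study Period". The protocol is Version 2.1, dated January 2025. No start or end date for recruitment is given anywhere.

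**The concern.** A participant who joins too late for a visit to fall before the end date has not dropped out. The visit was never going to take place. Section 4.7 foresees this for T3, but the table in section 4.8 does not carry the qualifier over. Applied as labelled, the row keeps such a participant in the denominator and can never place them in the numerator.

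Study attrition is one component of the composite feasibility outcome in section 4.6, and a red row is read as a reason to overhaul the design or the processes. A row that is lowered by the calendar could therefore send the planning of the definitive trial in the wrong direction. The same late recruits would lack the 12-month EQ-5D-5L needed for the QALY rehearsal (section 5) and, in the intervention arm, the 12-month adherence questionnaire (section 6).

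**Working it through.** The protocol states neither a cut-off date for follow-up nor an expected completion rate, so there is no figure of its own to reproduce. The check is calendar arithmetic.

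**Inputs from the protocol.** Last data collection 31 October 2025 (10.3); visits at 3, 6 and 12 months, window −14 to +28 days (4.7); thresholds 75% and 50% (4.8).

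**Input assumed.** Recruitment start and length, which the protocol does not give. Accrual is taken as uniform over six months, and the start date is varied.

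**Step 1: latest usable baseline.** At the early edge of the window, the latest baseline is the end date plus 14 days, minus the visit interval. 31 October 2025 + 14 days = 14 November 2025.

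| Visit | Latest baseline, early edge | Latest baseline, nominal date |
|---|---|---|
| T3 (12 months) | 14 November 2024 | 31 October 2024 |
| T2 (6 months) | 14 May 2025 | 30 April 2025 |
| T1 (3 months) | 14 August 2025 | 31 July 2025 |

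For the whole T3 window to be open, including the 4 weeks late, the baseline must fall by 3 October 2024 (31 October 2025 − 28 days = 3 October 2025, minus 12 months).

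**Step 2: ceiling on the 12-month row.** Completion over all recruited = f × r, where f is the share with a baseline by 14 November 2024 and r is true retention among them.

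- With r = 1, avoiding red needs f ≥ 50% and green needs f ≥ 75%.
- With r = 0.80, avoiding red needs f ≥ 0.50/0.80 = 62.5% and green needs f ≥ 0.75/0.80 = 93.8%.

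**Step 3: f under assumed uniform six-month accrual.** f = days from the start to 14 November 2024 inclusive, divided by days of accrual.

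| Assumed start | f | Row with no loss | Row with r = 0.80 |
|---|---|---|---|
| 1 April 2024 | 183/183 = 100% | 100%, green | 80%, green |
| 1 June 2024 | 167/183 = 91% | 91%, green | 73%, amber |
| 1 August 2024 | 106/184 = 58% | 58%, amber | 46%, red |
| 1 September 2024 | 75/181 = 41% | 41%, red | 33%, red |
| 1 November 2024 | 14/181 = 8% | 8%, red | 6%, red |
| 1 January 2025 or later | 0% | 0%, red | 0%, red |

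True retention of 80% would be green if truncation played no part. In the June and August rows it comes out amber and red.

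**Step 4: the earlier visits.** These are less exposed. With a six-month accrual from 1 January 2025 (181 days), 134 days fall by 14 May 2025, so T2 completion is at most 134/181 = 74% (amber). The T1 row is unaffected, because accrual ends before 14 August 2025.

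**The case against.** The strongest reply is that section 4.7 already makes T3 depend on the recruitment date. Read together with the table, late recruits are simply not scheduled for T3. No sentence says that they score as failures, and an analysis plan could settle the point. Part of this stands: the protocol foresaw truncation. But the table is the decision rule, it names its denominator, and nothing in it excludes people who were not due. An analyst who follows the row as written would count them.

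A reader might go further than the document allows in three ways.

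- **That the 12-month row will be red.** This depends on recruitment dates that the protocol does not give. The assumed schedules above give green, amber and red.
- **That recruitment had not begun in January 2025.** Sections 7, 8.1 and 10.2 place the start of recruitment in the future, and section 9 says "Ethical approval will be sort by Northumbria University and the NHS REC". Yet a Version 2.1 may be an amendment made during recruitment with older wording left in, and section 4.7 describes the questionnaires as already developed. Likewise, a 12-month study period equal to the 12-month follow-up leaves no recruitment window if taken literally. However, the summary field is undefined and may mean time per participant. These signs make truncation likely but do not prove it.
- **That the trial cannot answer its attrition question.** The 3- and 6-month rows are separate criteria with later cut-offs and still inform attrition.

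**Conclusion.** The concern holds in a limited form. The end date, the T3 schedule and the denominator of the follow-up rows are not reconciled. Anyone with a baseline after 14 November 2024 cannot have an in-window T3 but remains in the denominator, and the same applies to T2 after 14 May 2025 and T1 after 14 August 2025. This part rests only on the protocol's own dates.

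The effect on the traffic light is conditional. With no loss at all, the 12-month row is red if fewer than half of the recruits had a baseline by 14 November 2024, and it cannot be green if fewer than three quarters did. The range of ceilings from 100% down to 0% rests on assumed start dates and uniform six-month accrual. The documents do not show which case applies. This should be fixed before the criteria are applied. It does not invalidate the design.

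**What to change.** 1. In the three follow-up rows of section 4.8, replace *recruited participants* with *randomised participants whose nominal visit date falls on or before 31 October 2025*. For T3 this means a baseline by 31 October 2024. Use the same set for numerator and denominator, so that a participant with a baseline between 1 and 14 November 2024 who completes T3 early is in neither and is reported separately.
2. Report the numbers due and not due at each visit, and give the completion rate among those due with a 95% confidence interval.
3. Fix in advance a minimum number due. Below it, a row is recorded as not assessed rather than red.
4. State the recruitment start and end dates, and reconcile the 12-month study period in the summary with 12 months of follow-up.

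Alternatively, if T3 is wanted on everyone, define the end date in section 10.3 as last randomisation plus 12 months plus the 4-week late window.

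**Cost.** The denominator change needs no new data. The 12-month estimate and the 12-month QALY rehearsal would rest on fewer people, possibly none. If nobody was due, the change cannot recover 12-month retention and only prevents a misleading red. Since a progression criterion is altered, the change should be recorded as a protocol change, with ethical approval sought where necessary, as section 10.1 provides. The alternative lengthens the study.

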10.4 Confidentiality

Names and contact information will be held securely on password protected computer/servers. Participants will be given a unique participant trial identification (ID) number. This ID will be held in a separate secure file with access on a need-by-need basis only within the study team. A separate master file will be constructed linking participants to their unique trial identification number and will be kept secure at all times with access limited within the study team to the Chief investigators and trial statistician, others who require access will be determined on a case-by-case basis. Data for the feasibility study will be collected through the iSupport-PD study website, through an electronic case report form (CRF) with data stored on a secure password protected, purposely designed electronic database.

Transcripts will be anonymised and any potentially identifying information will be removed. The interview recordings will be destroyed once they are transcribed and checked. Transcription will be carried out by a member of the research team. The research team will not have details of who has been invited unless they express an interest to the research team.

Participants are free to withdraw at any point during the trial without any impact on their future health and care. Unless specifically withdrawn, participant data will be used up until the point of withdrawal.

11. Pathways to impact

